ClinicalTrials.gov Study Document

Study Protocol and Statistical Analysis Plan

Official Title

The Effectiveness of Passive Physiological Intervertebral Movements in Patients With Cervicogenic Headache: A Randomized Clinical Trial

NCT Number	Pending assignment - replace with the assigned NCT number before final public posting if required by PRS
Document Date	20 May 2026
Version	1.0
Study Status	Completed; retrospective ClinicalTrials.gov registration preparation
Sponsor/Institution	Jordan University of Science and Technology
IRB Approval	Jordan University of Science and Technology Institutional Review Board, Approval No. 73/148/2022

Public posting note: This document was prepared for ClinicalTrials.gov public posting. It does not include participant names or individual participant identifiers.

1. Protocol Synopsis

Condition	Cervicogenic headache
Study Design	Assessor-blinded, parallel-group randomized clinical trial
Allocation	Randomized allocation to two intervention arms
Intervention Model	Parallel assignment
Planned/Actual Enrollment	64 participants, 32 per arm
Setting	Outpatient physiotherapy departments of Jordan University of Science and Technology and King Abdullah University Hospital
Study Period	May 2022 to August 2025
Treatment Duration	Eight supervised sessions over four weeks
Assessment Time Points	Baseline, immediately after the four-week intervention, and three-month follow-up
Experimental Arm	Passive Physiological Intervertebral Movements plus therapeutic exercise
Comparator Arm	Therapeutic exercise alone

2. Background and Rationale

Cervicogenic headache is a secondary headache disorder associated with dysfunction in the cervical spine, particularly the upper cervical segments. Patients may experience headache, neck pain, restricted cervical movement, disability, psychological symptoms, and reduced quality of life. Therapeutic exercise and manual therapy are commonly used in physiotherapy management. Passive Physiological Intervertebral Movements are manual therapy techniques used to assess and improve segmental mobility. The study evaluated whether adding these movements to a standardized exercise program provides additional benefit compared with exercise alone.

3. Objectives

The primary objective was to determine the effect of adding Passive Physiological Intervertebral Movements to therapeutic exercise on headache pain intensity among participants with cervicogenic headache.

Secondary objectives were to evaluate between-group differences in headache frequency, neck pain intensity, neck-related disability, depression, anxiety, stress, and health-related quality of life at the post-intervention and follow-up assessments.

4. Study Design and Setting

This was a randomized clinical trial with two parallel groups. Participants were assigned to either Passive Physiological Intervertebral Movements plus therapeutic exercise or therapeutic exercise alone. The study was conducted in outpatient physiotherapy settings at Jordan University of Science and Technology and King Abdullah University Hospital. Outcome assessments were collected at baseline, four weeks, and three months.

5. Participant Identification and Eligibility Overview

Participants were screened using a standardized diagnostic process for cervicogenic headache based on clinical history and physical examination. Diagnostic confirmation included assessment of upper cervical dysfunction and symptom behavior consistent with cervicogenic headache. Individuals with contraindications to cervical mobilization or conditions that could confound assessment or treatment were excluded. Full eligibility criteria are entered separately in the ClinicalTrials.gov record.

6. Recruitment

Participants were recruited from physical therapy and rehabilitation services at King Abdullah University Hospital, university students, Ministry of Health hospitals, private physiotherapy centers, and the community. Recruitment approaches included social media advertisements, word of mouth, posters at Jordan University of Science and Technology, and private sector flyers.

7. Randomization and Allocation Concealment

After eligibility confirmation and baseline assessment, participants were randomly assigned to study groups using a random number generator. The randomization process was overseen by an independent researcher who was not involved in diagnosis, treatment, or outcome assessment. Sequentially numbered, opaque, sealed envelopes were prepared before recruitment and used to maintain allocation concealment.

8. Blinding

Outcome assessments were conducted by an assessor who was blinded to group allocation and was not involved in treatment delivery. Due to the nature of the manual therapy intervention, treatment providers were not blinded.

9. Interventions

9.1 Common Therapeutic Exercise Program

Both groups received the same standardized therapeutic exercise program. The program included deep cervical flexor activation using a chin-tuck exercise, scapular retraction, passive static self-stretching for the upper trapezius, levator scapulae, and sternocleidomastoid muscles, and active neck mobility exercises in flexion, extension, side flexion, and rotation. Participants were encouraged to continue the exercises at home.

9.2 Experimental Intervention

Participants in the experimental arm received Passive Physiological Intervertebral Movements in addition to the exercise program. The manual therapy intervention was individualized according to clinical findings and targeted the upper cervical joints, including C0-C1, C1-C2, and C2-C3, with the aim of restoring upper cervical mobility.

9.3 Comparator Intervention

Participants in the comparator arm received the same structured therapeutic exercise program without Passive Physiological Intervertebral Movements.

9.4 Treatment Schedule

Each participant received eight supervised treatment sessions over four weeks, with two sessions per week. Each session lasted approximately 15 to 20 minutes.

10. Outcomes and Assessment Schedule

Outcomes were assessed at baseline, immediately after the four-week intervention, and at three-month follow-up. The primary outcome was headache pain intensity measured using the Numeric Pain Rating Scale. Secondary outcomes were headache frequency per week, neck pain intensity, Neck Disability Index score, Depression Anxiety Stress Scale-21 stress, anxiety and depression scores, and Short Form-12

physical and mental component scores. Detailed outcome measure definitions are entered separately in the ClinicalTrials.gov record.

11. Sample Size

The sample size was calculated using power analysis based on headache pain intensity as the primary outcome. Using an effect size derived from a similar study, with power of 0.90 and alpha of 0.05, the required sample size was 64 participants, with 32 participants per group.

12. Data Collection and Management

Baseline demographic and clinical data were collected using a structured questionnaire. Clinical outcomes were collected using validated self-administered questionnaires and scales at the pre-specified assessment time points. Data were treated confidentially and stored securely. Hard-copy data were kept in a locked file cabinet, and electronic data were kept on a password-protected computer according to institutional procedures.

13. Safety Monitoring

Participants were screened for contraindications to cervical mobilization before enrolment. Participants were informed that participation was voluntary and that they could withdraw at any time without penalty. Any unexpected symptoms or adverse responses during treatment were to be managed by the study team according to clinical judgment and institutional procedures.

14. Statistical Analysis Plan

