14.4 Outcome Analysis

Multivariate analysis of variance was used to examine between-group differences in outcome measures at the assessment points. When multivariate tests were statistically significant, independent-samples t-tests were conducted for individual outcome variables. The significance level was set at $p < 0.05$, one-tailed. Analyses were performed using IBM SPSS Version 25.

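### The primary outcome has no primary time point and no adjustment across four weeks and three months, so the plan permits either result to be presented as the primary finding

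*Combined protocol and SAP*

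**What the plan says.** Section 3 states the aim without a time: "The primary objective was to determine the effect of adding Passive Physiological Intervertebral Movements to therapeutic exercise on headache pain intensity". Section 10 gives two post-baseline assessments, "Outcomes were assessed at baseline, immediately after the four-week intervention, and at three-month follow-up", and then defines the primary outcome without choosing between them: "The primary outcome was headache pain intensity measured using the Numeric Pain Rating Scale". Section 11 bases the sample size on the same outcome, again with no time: "with power of 0.90 and alpha of 0.05, the required sample size was 64 participants, with 32 participants per group". The effect size behind that number is not given; it is said only to come from a comparable earlier trial.

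The testing rule is in Section 14.4: "Multivariate analysis of variance was used to examine between-group differences in outcome measures at the assessment points". The t-tests depend on that result: "When multivariate tests were statistically significant, independent-samples t-tests were conducted for individual outcome variables". One level is given for everything: "The significance level was set at $p < 0.05$, one-tailed". No hierarchy, alpha split or other adjustment between the two times appears. The section does not say whether there is one MANOVA covering both times or one at each.

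Section 10 also refers the reader to the ClinicalTrials.gov record for detailed outcome definitions. The title page shows the NCT number as pending and the study as completed. The document is dated 20 May 2026, and the study period ended in August 2025.

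**The concern.** A benefit at the end of treatment and a benefit at three months are different conclusions. A reader of this document cannot tell which one the trial was meant to establish. If NPRS favours the experimental arm at only one of the two times, nothing written here prevents that time from being reported as the primary result. Two tests at the full level also give two chances of a false positive on the one outcome that is supposed to carry the trial's claim. Because the document was prepared after completion, it cannot itself show that a time point was fixed before the results were known.

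**Working it through.** **Inputs from the document.** Two post-baseline times (Section 10); one-tailed 0.05 per test and a significant MANOVA required before the t-tests (Section 14.4); 32 per arm, power 0.90, alpha 0.05 with sidedness not stated (Section 11); one primary and eight secondary scores, nine outcomes in all (Section 10).

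**Inputs assumed.** The correlation between the two times, the correlation between outcomes, the true effects on the secondary outcomes, and no loss to follow-up. The document gives none of these.

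**1. The plan's own figure.** The 64 participants cannot be reproduced, because Section 11 gives no effect size. Solving backwards with d = √(2/n) × (z for alpha + z for power) and √(2/32) = 0.25:
- one-sided: 0.25 × (1.645 + 1.282) = 0.73 (0.74 with the noncentral t);
- two-sided: 0.25 × (1.960 + 1.282) = 0.81 (0.82 with the noncentral t).

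These d values are back-solved assumptions, not figures from the plan.

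**2. Two tests of NPRS with no MANOVA precondition.** With independent times, the chance of at least one false positive is 1 − 0.95² = 0.0975. With correlation ρ it is 1 − Φ₂(1.645, 1.645; ρ), where Φ₂ is the bivariate normal distribution function. At ρ = 0.5 this is 1 − 0.9122 = 0.0878.

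| ρ | 0 | 0.3 | 0.5 | 0.7 | 0.8 | 0.9 |
|---|---|---|---|---|---|---|
| P(at least one false positive) | 0.0975 | 0.093 | 0.088 | 0.080 | 0.075 | 0.068 |

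The comparison is with the plan's own 0.05 for a single one-tailed test.

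**3. The same tests behind the MANOVA.** This was simulated with normal data, 32 per arm, nine outcomes at two times, correlation 0.4 between outcomes and 0.5 between times, and no true effect on NPRS. The MANOVA is Hotelling's T² = 16 × D′S⁻¹D (D is the vector of mean differences, S the pooled covariance matrix). It is referred to F = T² × (63 − p)/(62p) on p and 63 − p degrees of freedom. Here p = 9 for one MANOVA per time and p = 18 for a single MANOVA, each at 0.05. There were 40,000 runs; the Monte Carlo standard error is at most about √(0.09 × 0.91/40,000) = 0.0014.

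| True effect on all eight secondary outcomes | One MANOVA per time | Single MANOVA |
|---|---|---|
| none | 0.013 | 0.008 |
| 0.3 SD | 0.036 | 0.025 |
| 0.5 SD | 0.068 | 0.057 |
| 0.8 SD | 0.089 | 0.088 |

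The precondition holds the error below 5% when the secondary outcomes show little or no effect. It loses most of its force at 0.5 SD and nearly all of it at 0.8 SD.

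**4. Power under Holm, overall two-sided 0.05.** The smaller p-value must fall below 0.05/2 = 0.025. From the noncentral t with 62 degrees of freedom and noncentrality d × √(32/2) = 4d, power at a single time at that step is 0.84 for d = 0.82 and 0.74 for d = 0.74. If the effect is present at both times, the chance of at least one rejection is about 0.91 to 0.93 (d = 0.82) or 0.84 to 0.87 (d = 0.74), for correlations of 0.7 down to 0.5.

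**The case against.** The strongest reply is that NPRS is not freely tested twice: Section 14.4 allows t-tests only after a significant MANOVA. That is correct, and if no outcome differs the error is about 1%. A reader might take 8.8% as the error rate of the written procedure. The document does not support that, because the figure applies only when the MANOVA is absent or almost always significant. What remains is that the precondition neither ranks the two times nor protects NPRS once secondary outcomes respond.

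A reader might also infer that the plan counts a positive result at either time as success. It states no success rule; it permits that presentation but does not prescribe it.

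It is tempting to set these rates against the 2.5% that a two-sided 5% test allows in the favourable direction. That mixes in the one-tailed level, which is a separate issue. The effect of having two times is measured from 5%.

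The registry record may give a time frame. It cannot be seen here, so the point is that this document names none, not that none exists. With the number still pending after completion, an entry there would in any case not show that the choice came before the results.

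Finally, the late date might suggest that a time point was chosen from the results. Nothing in the document shows this; it only leaves the possibility open.

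Assessing at two times is ordinary practice and is not criticised here.

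**Conclusion.** The concern holds in this form: the document names a primary outcome without a primary time, applies one unadjusted level at both times, and so permits either result to carry the primary claim. That gap follows from the text and needs no assumption.

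Its size does depend on assumptions. Without the MANOVA precondition, the false-positive rate on the primary is about 6.8% to 9.75%, against the plan's 5%, for correlations of 0.9 down to 0. With the precondition it is about 1% if nothing differs and about 6% to 9% if the secondary outcomes have true effects of 0.5 to 0.8 SD, at assumed correlations of 0.4 between outcomes and 0.5 between times. The ambiguity over which conclusion is primary remains whatever the error rate. It should be resolved before the results are presented as confirmatory.

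**What to change.** Amend Section 14.4, and Sections 3, 10 and 11 to match.

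- If the 2022 IRB-approved protocol names a primary time point for NPRS, state it, cite that protocol as the source, and list the other time as secondary.
- If it names none, say so and do not choose one now. Test NPRS at both times under Holm at the trial's overall alpha, and report both estimates with 95% confidence intervals.
- In either case, test the primary outcome without requiring a significant MANOVA, so that the claim does not depend on the secondary outcomes.
- Label this as a change made after trial completion, and keep the description of the analysis originally performed.

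The cost is a small re-analysis and re-reporting, with no new data; it is more than a change of wording. Naming one time point costs no alpha. Under Holm at overall two-sided 0.05, power at one time at the 0.025 step is about 0.84 if d = 0.82 or 0.74 if d = 0.74, on back-solved effect sizes and with no loss to follow-up. It is higher for at least one rejection if the effect is present at both times.

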14.1 Analysis Population

Analyses were based on participants with available data at each assessment time point. The number of participants included in each outcome analysis was reported for each assessment point.

14.2 Descriptive Statistics

Continuous variables were summarized using means and standard deviations. Categorical variables were summarized using frequencies and percentages. Baseline characteristics and baseline clinical measures were compared between groups to assess group comparability after randomization.

14.3 Baseline Comparisons

Independent-samples t-tests were used to compare continuous baseline variables between groups. Chi-square tests were used to compare categorical baseline variables between groups.

14.4 Outcome Analysis

Multivariate analysis of variance was used to examine between-group differences in outcome measures at the assessment points. When multivariate tests were statistically significant, independent-samples t-tests were conducted for individual outcome variables. The significance level was set at $p < 0.05$, one-tailed. Analyses were performed using IBM SPSS Version 25.

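### The primary outcome is tested only through a joint MANOVA followed by gated t-tests, and no between-group difference in headache pain with a confidence interval is planned

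*Combined protocol and SAP*

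**What the plan says.** Section 3 frames an estimation question: "The primary objective was to determine the effect of adding Passive Physiological Intervertebral Movements to therapeutic exercise on headache pain intensity". Section 10 agrees: "The primary outcome was headache pain intensity measured using the Numeric Pain Rating Scale". It lists eight secondary scores besides (headache frequency, neck pain, Neck Disability Index, three DASS-21 scores and two SF-12 component scores), which makes nine outcomes in all. Assessments after baseline are at four weeks and three months.

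Section 14.4 holds the whole inferential plan. Its first step is "Multivariate analysis of variance was used to examine between-group differences in outcome measures at the assessment points". The second step, t-tests on single outcomes, is taken only when the multivariate test is significant. The criterion is "The significance level was set at $p < 0.05$, one-tailed".

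Section 14.2 plans means and standard deviations as summaries. Section 11 sizes the trial thus: "Using an effect size derived from a similar study, with power of 0.90 and alpha of 0.05, the required sample size was 64 participants". It gives no value for the effect, no SD and no sidedness. No section plans a between-group difference, a confidence interval or a reference amount for reading the size of a result.

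**The concern.** The objective asks how large the effect on headache pain is, but the plan provides only tests. Two consequences follow.

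- **The gate opens.** A modest pain difference can cross the t-test threshold and be described as significant. Nothing planned would show how uncertain it is.
- **The gate stays shut.** The plan has no further between-group analysis of the primary outcome. A real effect on pain could be diluted among eight other scores and end with no comparative result at all.

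At stake is whether the report can tell a clinician how much pain relief the added manual therapy gives, and how precisely that is known.

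**Working it through.** **Inputs from the documents.** 32 per arm, power 0.90, alpha 0.05 (Section 11); one-tailed 0.05 (Section 14.4); nine outcomes (Section 10).

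**Assumptions.** Complete data; a MANOVA at 0.05 on the nine outcomes at one time point; NPRS SD of 1.5 to 2.5 points, used only to convert to points.

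**1. The plan's own figure.** The 64 cannot be reproduced, because neither effect size nor SD is given. It can be back-solved. The standard error in SD units is √(2/32) = 0.25, with 62 degrees of freedom. By the normal approximation:

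- one-sided: d = (1.645 + 1.282) × 0.25 = 0.73
- two-sided: d = (1.960 + 1.282) × 0.25 = 0.81

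The noncentral t gives 0.740 and 0.823.

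**2. Smallest observed difference that is significant in the t-test.** This is the critical t times 0.25.

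- one-tailed: 1.670 × 0.25 = 0.417 SD
- two-tailed: 1.999 × 0.25 = 0.500 SD

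Under the one-tailed test as written, the share of the implied design effect is:

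- sized one-sided: 0.417/0.740 = 0.56
- sized two-sided: 0.417/0.823 = 0.51

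If both sizing and testing were two-sided, it would be 0.500/0.823 = 0.61.

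**3. Precision at that threshold.** The two-sided 95% half-width is 0.500 SD, so the interval is 0.417 ± 0.500, or −0.08 to 0.92 SD. In points:

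| Assumed SD | One-tailed threshold | 95% interval at the threshold |
|---|---|---|
| 1.5 | 0.63 | −0.12 to 1.38 |
| 2.0 | 0.83 | −0.16 to 1.83 |
| 2.5 | 1.04 | −0.21 to 2.29 |

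**4. The MANOVA gate.** With p = 9 outcomes and N = 64, the Hotelling critical value is T² = F(0.95; 9, 54) × 9 × 62/54 = 2.059 × 10.33 = 21.3. If pain alone differs and the outcomes are uncorrelated, T² = 16d² (from 32 × 32/64 = 16). An observed d of √(21.3/16) = 1.15 is then needed to pass.

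**5. Chance of passing the gate when the true effect is the implied design effect.** Same illustrative case, noncentral F with 9 and 54 degrees of freedom and noncentrality 16d²:

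- d = 0.74: noncentrality 8.76, probability about 0.43
- d = 0.82: noncentrality 10.76, probability about 0.53

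The t-test alone would have power 0.90 for the same effect, if sized and tested with the same sidedness.

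**The case against.** A reader might infer that a result about half the design effect would be reported as effective. The documents do not support that. A pain difference of 0.42 SD reaches a t-test only if the MANOVA is significant. If pain alone differs and outcomes are uncorrelated, that takes about 1.15 SD. With other effects or correlations the requirement moves either way, so such a result could be called significant, not that it would be.

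Nor do the documents state a rule for declaring the treatment effective. That benefit is decided by a p-value alone is an inference, although p is the only criterion given.

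Three more objections stand in part.

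- **The ratio is ordinary.** When sizing and testing use the same sidedness, a threshold at 56% to 61% of the design effect is found in any two-arm trial with 90% power. It is not a fault of this plan. It shows only why an estimate and interval are needed.
- **The lower limit below zero** comes from setting a one-tailed 0.05 test beside a two-sided 95% interval. It is not separate evidence of a missing estimate.
- **The information is partly recoverable.** If means, SDs and numbers analysed are reported by arm after baseline, a reader can compute a raw difference and interval. That leaves the primary result to the reader and does not make it part of the plan.

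None of this supplies a planned NPRS difference or interval, or a between-group result for the primary outcome when the MANOVA is not significant.

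**Conclusion.** The point holds, as a gap in the analysis of the primary outcome that should be closed; it does not show that an ineffective treatment will be called effective. Section 14.4 makes any separate test of headache pain conditional on a nine-outcome joint test, and no section plans the between-group NPRS difference with an interval.

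A difference of about 0.42 SD, 51% to 56% of the implied design effect, could be called significant with its imprecision unreported. In the illustrative case, a true effect of 0.74 to 0.82 SD would leave the primary outcome without a between-group result about 47% to 57% of the time (1 − 0.53 to 1 − 0.43).

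The design effect is back-solved, with its sidedness unknown. The gate probabilities rest on uncorrelated outcomes with only pain differing, and would change with other correlations or effects. The SD-unit figures do not depend on the assumed NPRS SD; the figures in points do.

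**What to change.** In Section 14.4, make the primary result the between-group difference in headache NPRS, in points, with a two-sided 95% confidence interval at each assessment point. Report it whatever the MANOVA or the t-tests show, and base the conclusion on the estimate and interval.

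In Section 11, state the effect size and SD behind the 64 and express them in NPRS points, for context only. Section 11 says the effect came from a similar study, not that it is clinically worthwhile, so it should not become a threshold for claiming benefit. Requiring the point estimate to reach it would cut the chance of a positive claim to about 50% when the true effect equals it, because the estimate falls short about half the time.

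Section 1 gives the trial's status as completed. Label this analysis, and any benchmark not documented beforehand, as post hoc.

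The cost is a few sentences and one table, with no new data. The small downside is that a borderline one-tailed result would be shown with an interval that includes zero.

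### After a significant MANOVA, eight secondary outcomes at two visits are each tested unadjusted at one-tailed 0.05, so false secondary claims are uncontrolled once any outcome truly responds

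*Combined protocol and SAP*

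**What the plan says.** Section 14.4 gives the whole decision rule in three steps.

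- Multivariate step: "Multivariate analysis of variance was used to examine between-group differences in outcome measures at the assessment points".
- Follow-up: "When multivariate tests were statistically significant, independent-samples t-tests were conducted for individual outcome variables".
- Threshold: "The significance level was set at $p < 0.05$, one-tailed".

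Section 10 names one primary outcome: "The primary outcome was headache pain intensity measured using the Numeric Pain Rating Scale". It then lists the secondaries: "Secondary outcomes were headache frequency per week, neck pain intensity, Neck Disability Index score, Depression Anxiety Stress Scale-21 stress, anxiety and depression scores", followed by the SF-12 "physical and mental component scores". That is six plus two, or eight. Section 3 sets their comparison, up to and including "health-related quality of life at the post-intervention and follow-up assessments", at two post-baseline visits.

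The document contains no Bonferroni or Holm adjustment, testing order or division of alpha between visits, and it does not label the secondaries exploratory. It also does not say how many MANOVAs are run, which outcomes enter each, or which visit is primary.

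**The concern.** A MANOVA followed by unadjusted t-tests gives weak control only: the error rate is held when no outcome differs between arms. The trial was run in the hope that headache pain would differ. If pain responds and sits in the MANOVA, it can make the multivariate test significant by itself, and the eight secondaries at that visit are then each tested at one-tailed 0.05 (equal to two-sided 0.10) with nothing further to limit false claims.

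At stake is how secondary results on neck pain, disability, depression, anxiety, stress or quality of life are read. The plan gives them the same multivariate step and threshold as the primary, so a significant secondary result would look as firmly established as one on pain.

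**Working it through.** **Inputs from the documents.** 32 per arm (Sections 1 and 11); power 0.90 and alpha 0.05 (Section 11); one-tailed 0.05 for outcome tests (Section 14.4); one primary and eight secondary outcomes (Section 10); two post-baseline visits (Sections 3 and 10). Secondary tests: 8 × 2 = 16.

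**The plan's own figure.** Section 11 states "with power of 0.90 and alpha of 0.05, the required sample size was 64 participants, with 32 participants per group" but gives no numerical effect size, so 64 cannot be reproduced. It can be solved backwards with d = (z for alpha + z for power) × √(2/32):

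- one-sided 0.05: (1.645 + 1.282) × 0.25 = 0.73 (0.74 with the t distribution);
- two-sided 0.05: (1.960 + 1.282) × 0.25 = 0.81 (0.82 with the t distribution).

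The implied design effect is therefore about 0.74–0.82.

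**Simple reference values.** With independent tests and no multivariate step, the chance of at least one false positive is 1 − 0.95^8 = 33.7% for one visit and 1 − 0.95^16 = 56.0% for both. These are upper reference points, not estimates for this plan.

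**Simulation of the rule.** Assumptions that the documents do not settle: nine outcomes including NPRS in one MANOVA per visit; MANOVA tested at 0.05; equal correlation between outcomes; between-visit correlation 0.5; a true effect on NPRS only, the same at both visits. There were 6,000 trials per row (standard error at most √(0.25/6000) = 0.65 percentage points). A false claim is any secondary significant in the direction of benefit at a visit where the MANOVA is significant.

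| Outcome correlation | d on NPRS | MANOVA significant, per visit | Any false secondary claim, both visits | Same, without the MANOVA step | Same, MANOVA plus threshold 0.05/16 |
|---|---|---|---|---|---|
| 0 | 0 | 4.9% | 6.6% | 51.8% | 1.9% |
| 0 | 0.73 | 41.5% | 32.1% | 52.5% | 4.1% |
| 0 | 0.82 | 52.4% | 37.3% | 52.7% | 4.4% |
| 0 | 1.2 | 89.5% | 49.6% | 51.9% | 4.3% |
| 0.3 | 0 | 4.8% | 5.3% | 42.8% | 1.7% |
| 0.3 | 0.73 | 54.3% | 29.5% | 41.6% | 4.0% |
| 0.3 | 0.82 | 66.0% | 34.6% | 42.3% | 3.9% |
| 0.3 | 1.2 | 96.6% | 41.4% | 41.8% | 4.8% |
| 0.5 | 0 | 4.7% | 4.2% | 34.8% | 1.4% |
| 0.5 | 0.73 | 72.1% | 29.3% | 34.7% | 3.6% |
| 0.5 | 0.82 | 83.4% | 32.1% | 35.3% | 4.1% |
| 0.5 | 1.2 | 99.6% | 35.1% | 35.1% | 3.6% |

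Three things follow.

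1. With no effect anywhere, the rule works: 4–7% over both visits.
2. At the design effect, the rate over both visits is 29–37% in the table and up to 38% in repeat runs. For a single visit it is about 17–22%.
3. The rate approaches the value without the MANOVA step as the pain effect grows. At d = 1.5 the MANOVA is significant in 99–100% of trials, and the rate is about 34%, 27% and 22% per visit, or about 52%, 42% and 35% over both, for correlations 0, 0.3 and 0.5.

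A threshold of 0.05/16 = 0.0031 brings every row to 5% or below.

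**The case against.** The other side has several fair points.

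- **The multivariate step is not worthless.** At d = 0.73 and uncorrelated outcomes, it lowers the rate over both visits from 52.5% to 32.1%. A reader might infer that protection vanishes whenever pain responds. That is nearly true for a very large effect, but not at the effect that the sample size implies.
- **The 56% figure is tempting.** It ignores the multivariate step and treats the same person's scores at four weeks and three months as independent. It should not be quoted as this plan's error rate.
- **The layout is unstated.** Section 14.4 refers to outcome measures generally, so including NPRS is the natural reading, but the text does not confirm it. If NPRS were analysed separately, a pain effect alone would not make the MANOVA significant and the simulated figures would not apply. A true effect on any included secondary would still lead to unadjusted tests of the others.
- **The plan promises no 5% family-wise rate for secondaries.** Section 14.4 sets a significance level only, and strong control over secondaries is stricter than many trials adopt. That defence would be sufficient if the secondaries were labelled exploratory. They are not.

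These points reduce the size of the problem. They do not remove it: every simulated case in which pain responds is well above 5%.

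**Conclusion.** The concern stands in this form: the plan controls false secondary claims only when no outcome differs between arms, and has no control over the 16 secondary tests once any outcome responds. At the design effect (d about 0.74–0.82), the chance of at least one false secondary claim is about 17–22% per visit and 29–38% over both, against 4–7% over both when nothing differs. At d = 1.5 it is about 35–52% over both.

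These figures rest on NPRS being in one MANOVA per visit, a multivariate level of 0.05, between-outcome correlation 0–0.5 and between-visit correlation 0.5. At a between-outcome correlation of 0.7 the rate over both visits is still 27–28% for d from 0.73 to 1.2. The absence of adjustment after the MANOVA does not depend on any of these assumptions; the percentages do.

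A reader might go further and infer that a given significant secondary result in this trial is probably false, or that the pain result is undermined. The documents contain no results, and neither conclusion follows from the testing rule.

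**What to change.** 1. Test NPRS on its own, not through the MANOVA. This also helps the primary analysis: at d = 0.73 the multivariate test is significant at a given visit in only 42–72% of trials (correlation 0–0.5), although the trial was sized for 90% power.
2. For the secondaries, choose one route and state it:
   - report all eight at both visits as exploratory estimates with 95% confidence intervals and no significance claim; or
   - if claims are wanted, apply Holm across all 16 secondary tests after a significant NPRS result (smallest p-value compared with 0.05/16 = 0.0031), and report those that fail as estimates with intervals.
3. State which visit or visits the NPRS decision uses. None is named as primary and Section 1 describes the trial as completed, so disclose this choice, and the whole change, as post hoc.

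Whether tests should be one-tailed or two-sided is a separate question; either route works once that is settled. The cost is SAP wording and recomputed p-values on existing data. The downside is that some nominally significant secondary results may lose that label.
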